Muscle: Muscle events have been associated with statins ([Thompson 2003](#)) and other lipid-lowering therapies and are mentioned in the product information for those products. The exact mechanism in the development of muscle events is unclear. Bempedoic acid is a prodrug which needs to be converted by an acyl-CoA synthetase (ACS) to a coenzyme A (CoA) ester (ETC-1002-CoA). The specific ACS known to convert bempedoic acid into its active form is not present in skeletal muscle. This suggests that bempedoic acid may not lead to an increase in muscular side effects when given in conjunction with statins. Nonetheless, muscle symptoms through AE review, CK elevations, and symptoms of potential myopathy will be closely monitored. More detailed investigation will occur if results exceed 5 x ULN (see [Section 11.1.6.3.2](#)).

Diabetes and Hyperglycemia: New onset diabetes has been associated with the use of statins and is dose related. The product information for statins mentions hyperglycemia increased HbA_{1C} and increases in fasting glucose as potential adverse reactions. Hyperglycemia occurred in 10.8% (n = 10) of the placebo treated patients vs none of the bempedoic acid 180 mg treated patients in the Phase 2 program. Regardless, new onset diabetes through AE monitoring will be captured and summarized for this study and across all of the bempedoic acid studies. Clinical safety laboratories will also be evaluated during the studies including HbA_{1C}, and fasting glucose.

Renal: Nonclinical studies have demonstrated nephrotoxic effects on tubular cells of some lipid-modifying agents. In the Phase 2 program, creatinine elevations >25% over baseline occurred in 1 subject in the bempedoic acid 80 mg, 2 in the 180 mg, 1 in the 180 mg + ezetimibe, 1 in the 240 mg, and 3 in the 240 mg + baseline statin. In most cases, this elevation occurred at the end of the study and the values were not repeated and the events were not considered related. In 1 case, repeat values were obtained and the subject's creatinine was returning to baseline by Week 12. None exceeded a serum creatinine >1.8 mg/dL. No subjects withdrew due an AE of increased creatinine. In the Phase 3 program, repeat evaluation of creatinine will occur and patients exceeding protocol-specified values will be withdrawn from study medication (see [Section 11.1.6.3.2](#)). Patients will be monitored beyond the

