Cases of new onset of diabetes will be recorded as AEs and will be summarized using the appropriate SOC. These events will be summarized by severity and relationship to study drug for each treatment group. Glucose and HbA_{1C} will be monitored at baseline and at Weeks 12, 24, and 52, and be summarized.

Renal Safety

Baseline eGFR will be summarized by treatment group for actual value and for baseline eGFR categories. Shift tables of eGFR category from baseline over the study, will be provided by treatment group. Shift tables of urine protein (negative/positive) from baseline over the study, will be provided by treatment group. Values of CK over the study will be summarized by treatment group and by baseline eGFR category. Finally, muscle-related AEs will be summarized by treatment group and by baseline eGFR category.

Neurocognitive Events

Neurocognitive events will be identified and evaluated by routine safety monitoring of PE findings and AEs. Summarization of neurocognitive events will occur using prespecified MedDRA terms and will be performed by SOC, severity, and relationship to study drug for each treatment group.

Clinical Endpoints

Clinical endpoints using standardized definitions will be adjudicated by an independent blinded expert CEC for all ongoing Phase 3 studies in the bempedoic acid program. Investigator-reported clinical endpoints and adjudicated clinical endpoints will be summarized by event type and treatment group. Additional details regarding the clinical endpoints and their definitions will be included in CEC Charter.

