11. DEMOGRAPHIC AND OTHER BASELINE CHARACTERISTICS

Demographic data and other baseline characteristics will be summarized by treatment group for the FAS.

No statistical testing will be carried out for demographic or other baseline characteristics.

The following demographic and other baseline characteristics will be reported for this study:

- Age (years) - calculated relative to date of randomization
- Age category (<65 years vs. ≥65 years and < 75 years vs. ≥75 years)
- Gender
- Race
- Ethnicity
- Region (US vs. Canada vs. EU)
- Stratification factor
- CV risk (ASCVD only; HeFH (with or without ASCVD))
- Baseline statin intensity (high intensity; moderate intensity; low intensity)
- Weight (kg)

Statistical Analysis Plan

- Height (cm)
- BMI (kg/m²)
- BMI category (< 25 vs. 25 - < 30 vs. ≥ 30 kg/ m2)
- Baseline Laboratory Results (Total Cholesterol, LDL-C, HDL-C, Triglycerides, Non-HDL-C, Apolipoprotein B, and hsCRP)
- Baseline LDL-C category (<130 mg/dL, ≥130 and < 160 mg/dL, or ≥160 mg/dL)
- Baseline eGFR (normal: ≥90 mL/min/1.73m²; mild Renal Impairment: 60-89 mL/min/1.73m²; moderate Renal Impairment: 30-59 mL/min/1.73m², and severe Renal Impairment (15-29 mL/min/1.73m²)
- History of diabetes (Yes vs. No)
- History of hypertension (Yes vs. No)
- Baseline Vital Signs (systolic blood pressure (SBP) and diastolic blood pressure (DBP))
- Alcohol consumption (Non-Drinker, Former Drinker, or Current Drinker)
- Tobacco use (Never Used, Former User, or Current User)

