18.4. SAFETY LABORATORY EVALUATIONS

Results from the central laboratory will be included in the reporting of this study for Hematology, Blood Chemistry, Lipids, Coagulation, HbA1C, hsCRP and Urinalysis. A list of laboratory assessments to be included in the outputs is included in Protocol, Section 11.1.6.1.

Presentations will use SI Units and conventional units.

Quantitative laboratory measurements reported as “< X”, i.e. below the lower limit of quantification (BLQ), or “> X”, i.e. above the upper limit of quantification (ULQ), will be converted to X for the purpose of quantitative summaries, but will be presented as recorded, i.e. as “< X” or “> X” in the listings.

The formula to calculate eGFR is: $eGFR = 186 \times (\text{Creatinine} / 88.4)^{-1.154} \times (\text{Age})^{-0.203} \times (0.742 \text{ if female}) \times (1.210 \text{ if black})$, where creatinine is in mmol/L.

Summaries for all lab results, including unscheduled visit values, will be included for below analyses:
 Observed and change/percent change from baseline by visit (for quantitative measurements).

Shift from baseline by visit according to normal ranges.

Shift from baseline according to normal ranges for HbA1c and glucose by history of diabetes and visit.
 eGFR and values of CK will be summarized by treatment group and by baseline eGFR categories (low, normal, high).

Potential Hy’s law cases (>3 × ULN for either ALT or AST AND Total Bilirubin >2 × ULN in the setting of no known other cause) will be tabulated and listed.

Laboratory abnormalities in parameters of interest

- ALT or AST (> 3x ULN , >5xULN)
- TB (>2x ULN)
- CK (> 5x ULN) and (>10x ULN)
- Fasting Blood Glucose (≤50 mg/dL, ≥126 mg/dL) by history of diabetes
- HbA1c (≥6.5%) by history of diabetes
- Creatinine (change from baseline for >1 mg/dL)
- eGFR (< 15 mL/min/1.73m², 15 –< 30 mL/min/1.73m²)
- Hgb (decrease from baseline for ≥2 g/dL)
- Hgb (<8 g/dL)

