18.4.1. LABORATORY REFERENCE RANGES AND MARKEDLY ABNORMAL CRITERIA

Quantitative laboratory measurements will be compared with the relevant laboratory reference ranges in SI units and categorized as:

Low: Below the lower limit of the laboratory reference range.

Normal: Within the laboratory reference range (upper and lower limit included).

High: Above the upper limit of the laboratory reference range.

In addition to the high and low quantitative laboratory assignments, Hy's law criteria ($\geq 3 \times \text{ULN}$ for either ALT or AST, with accompanying total bilirubin $> 2 \times \text{ULN}$ in the absence of other known causes) will be used to identify potential Hy's law cases.

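### SAP 18.4 groups and shifts eGFR by laboratory reference range, not by the SAP's own renal categories; it omits two renal tables planned in protocol 12.8, and its only creatinine count cannot register rises of about 25%

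*SAP*

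**What the plan says.** Protocol 12.8, under renal safety, states: "Shift tables of eGFR category from baseline over the study, will be provided by treatment group". It also plans CK values and muscle-related adverse events by baseline eGFR category. Protocol 12.1 lets the SAP override the protocol where the two differ on analysis.

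SAP 11 sets out renal categories for the baseline table: normal at ≥90, then "mild Renal Impairment: 60-89 mL/min/1.73m²; moderate Renal Impairment: 30-59 mL/min/1.73m²", then severe at 15-29.

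SAP 18.4 uses another scheme: "eGFR and values of CK will be summarized by treatment group and by baseline eGFR categories (low, normal, high"). Its shift tables are described as "Shift from baseline by visit according to normal ranges", and SAP 18.4.1 gives the meaning: "Low: Below the lower limit of the laboratory reference range". The renal threshold counts are "Creatinine (change from baseline for >1 mg/dL") and eGFR in two bands, "eGFR (< 15 mL/min/1.73m²" and 15 to <30. Observed values, change and percent change by visit are planned for every quantitative laboratory measure.

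Protocol 11.4 gives the Phase 2 background: "creatinine elevations >25% over baseline occurred in 1 subject in the bempedoic acid 80 mg" group, with further cases at 180 mg (2), 180 mg plus ezetimibe (1), 240 mg (1) and 240 mg plus statin (3). None had creatinine above 1.8 mg/dL.

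**The concern.** Renal events are a named adverse event of special interest. Long-term safety over 52 weeks is a tertiary objective, and the completed studies described in protocol 4.2.3 dosed for up to 12 weeks. The renal tables should therefore show movement between levels of renal function, and whether CK elevations and muscle events concentrate in patients with impairment.

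A reference-range split does the first job poorly. It gives the second only for CK and only in coarse groups. The muscle-event table is not named at all. Because the SAP governs, a programmer following its text would not produce the tables the protocol describes. The creatinine count is also set at a size of change well above the one that drew attention in Phase 2.

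**Working it through.** The plan states no figure to reproduce here. The check compares the sections and then works through the thresholds.

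**1. Protocol 12.8 against the SAP**

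| Protocol 12.8 | SAP text |
|---|---|
| Baseline eGFR by value and category | SAP 11, with defined categories |
| Shift tables of eGFR category | 18.4: normal-range shifts only |
| CK by baseline eGFR category | 18.4: kept, but by low/normal/high |
| Muscle-related AEs by baseline eGFR category | Not named: 18.1.1 uses the 17.2.4 subgroups, which omit eGFR; 18.1.6 breaks AESIs down by category, SOC, PT, severity and relationship |

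**2. What a reference-range split can separate**

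Entry excludes eGFR <30 at screening (protocol 7.2), so baseline should span the normal, mild and moderate categories. Separating three groups needs cuts at 90 and 60; one lower limit supplies a single cut. The documents do not give the limit, so I take two assumed values:

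- Limit 90: low pools mild (60-89) with moderate (30-59).
- Limit 60: the group at or above the limit pools ≥90 with 60-89.

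The SAP equation makes eGFR proportional to creatinine^-1.154, so a 25% creatinine rise multiplies eGFR by 1.25^-1.154 = 0.773.

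| Baseline eGFR | After +25% creatinine | SAP 11 category | Limit 90 (assumed) | Limit 60 (assumed) |
|---|---|---|---|---|
| 90 | 69.6 | changes | changes | no change |
| 75 | 58.0 | changes | low to low | changes |
| 60 | 46.4 | changes | low to low | changes |
| 45 | 34.8 | same | low to low | low to low |

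None of these reaches the <30 flag. That flag registers a 25% creatinine rise only if baseline eGFR is below 30/0.773 = 38.8.

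**3. The creatinine count**

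The percent rise needed for +1 mg/dL is 100 divided by baseline creatinine in mg/dL.

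| Baseline (mg/dL) | 25% rise (mg/dL) | Rise needed to exceed +1 mg/dL |
|---|---|---|
| 0.8 | 0.20 | >125% |
| 1.0 | 0.25 | >100% |
| 1.2 | 0.30 | >83% |
| 1.5 | 0.375 | >67% |
| 4.0 | 1.00 | >25% |

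The highest entry-eligible baseline comes from solving 30 = 186 × Cr^-1.154 × age^-0.203 × (0.742 if female) × (1.210 if black). Over assumed ages 18 to 75, both sexes and both race terms, it runs from 1.76 to 3.45 mg/dL. Ages above 75 only lower it. Even at 3.45, a 25% rise is 0.25 × 3.45 = 0.86 mg/dL, below the threshold; the smallest countable rise there is 29%.

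The Phase 2 cases number 1 + 2 + 1 + 1 + 3 = 8, with a ceiling of 1.8 mg/dL. To exceed +1 mg/dL with a final value of at most 1.8, baseline must be below 0.8 and the rise above 125%.

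**4. Unit reading**

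SAP 18.4 divides creatinine by 88.4 but gives its unit as mmol/L. Read literally, 0.0884 mmol/L in a 65-year-old non-black man gives an eGFR of about 231,000; read as 88.4 µmol/L (1.0 mg/dL) it gives 79.7. I used the second reading.

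**The case against.** The strongest reply is that renal change is covered elsewhere. Creatinine change and percent change are summarised by visit, and SAP Appendix 1 sets the statistics to include quartiles and the maximum. Normal-range shifts cover creatinine as well as eGFR. Values under 30 and under 15 are counted, and renal preferred terms are tabulated as AESIs. The DMC receives tables of laboratory abnormalities and chemistry boxplots. All of this stands. A reader might infer that eGFR is reported only as low/normal/high, or that 25% creatinine rises are missed altogether. Neither is supported: low/normal/high is the baseline grouping for the eGFR and CK summaries, and what is absent is a count of patients above a relative cut.

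Second, the >25% cut is Phase 2 background. Protocol 11.4 adds that most of those values were not repeated and that the events were not considered related. Protocol 12.8 plans no creatinine threshold table, so the lack of one is limited sensitivity, not a departure.

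Third, silence in the SAP is not clearly a difference that overrides the protocol, and SAP 8 refers to table templates that are not part of the documents. The omitted tables may exist there. That lowers certainty about what was produced, but leaves the conflict between SAP 11 and SAP 18.4 in place.

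A dramatic example is also tempting. A 60-year-old non-black man going from 1.0 to 2.0 mg/dL falls from eGFR 81.0 to 36.4 and trips neither flag. But he sits exactly on the creatinine boundary (2.01 would count), and calling him low at both visits assumes a lower limit of 90. A patient starting at 30-59 who loses more than half would always be flagged below 30.

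**Conclusion.** The point holds as an inconsistency with practical consequences for descriptive safety tables. The SAP carries two eGFR schemes. The one chosen for grouping and shifts cannot separate normal, mild and moderate function wherever the lower limit lies, and two protocol 12.8 analyses are not named in the governing text. The creatinine count cannot register a rise of about 25% at any entry-eligible baseline, under the SAP equation with the unit read as µmol/L. This treats baseline as equal to the screening limit; a later baseline could be somewhat higher, but it would have to reach 4.0 mg/dL to matter.

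Which patients are fixed in the low row depends on an unstated reference limit. The individual sizes of the 8 Phase 2 rises are not given beyond exceeding 25%.

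The documents do not support saying that a renal signal would go unseen. Nor do they say this is the first 52-week controlled exposure: they state only that completed studies dosed for up to 12 weeks, and they mention other ongoing Phase 3 studies. The efficacy analyses are unaffected, and SAP 18 plans no formal comparison of safety data by default.

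**What to change.** In SAP 18.4:

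1. Replace the low/normal/high grouping with the SAP 11 categories plus <15, both for the baseline grouping of eGFR and CK and for eGFR shift tables by treatment group.
2. Restore muscle-related adverse events by baseline eGFR category, as in protocol 12.8.
3. Beside the >1 mg/dL line, add a descriptive count of patients with creatinine more than 25% over baseline, labelled as an addition and not a protocol commitment.

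The creatinine unit in the eGFR formula should be corrected in the same edit.

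The cost is a few extra tables from data already collected. The >25% count will include some transient rises in both arms, so it should be read by comparing arms. The SAP addendum shows that unblinding has already taken place and lists no renal table. If these tables were not run, items 1 and 2 can be reported as protocol-planned (with the choice of the SAP 11 cut-points, and the use of <15, disclosed), and item 3 should be labelled post hoc.

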- Patients continuing to exceed the TG threshold after maximizing the standard-of-care triglyceride-lowering therapy will be discontinued from IMP treatment and will be asked to continue to be followed for safety using the protocol-specified visit schedule.

Monitoring and Management of Potential AEs and Adverse Events of Special Interest (AESI)

Adverse Events Associated with Experience with Bempedoic Acid to Date:

Potential AEs:

Based on findings in nonclinical models, potential AEs include reversible hypoglycemia and metabolic acidosis. Patients will be educated on the signs and symptoms of hypoglycemia and asked to report the experienced signs and symptoms to the investigator. Investigator confirmed occurrences of hypoglycemia will be reported as AEs. Potential cases of reversible hypoglycemia and metabolic acidosis will be identified by routine safety monitoring of AEs and clinical safety laboratories.

Musculoskeletal Safety:

Patients with CK abnormalities will also be reviewed for any other lab changes, such as creatinine, and any reported AEs or SAEs. Musculoskeletal events will be identified and evaluated by routine safety monitoring of PE findings and AEs.

Diabetes and Hyperglycemia:

Cases of new onset of diabetes will be recorded as AEs. Clinical laboratories, including HbA_{1C} and glucose will also be evaluated across treatment groups during this study and all ongoing studies to identify potential cases of new onset of diabetes

Neurocognitive Events:

Neurocognitive events will be identified and evaluated by routine safety monitoring of PE findings and AEs.

Clinical Endpoints:

Clinical endpoints will be monitored and adjudicated by an independent expert CEC for this study and other ongoing studies in the bempedoic acid program.

Routine cardiovascular monitoring will include review of cardiovascular AEs, SAEs, (both as adjudicated by the CEC), standard vital signs, and ECGs.

Additional details regarding safety monitoring are included in [Section 11.1.6.3.1](#) through [Section 11.1.6.4](#).

Further details on occurrence and monitoring are available in the Investigator's Brochure (IB).

Statistical methods:

Sample Size

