and S2) may be extended up to 4 weeks to allow for a repeat qualifying BP assessment following adjustment of BP medication(s), provided that the patient has been on a stable dose of the BP medication for a minimum of 2 weeks prior to randomization and the repeat BP measurements do not meet the exclusion criteria.

6. Hemoglobin A_{1C} (HbA_{1C}) $\geq 10\%$ at Week -5 (Visit S1)
7. Uncontrolled hypothyroidism, including thyroid-stimulating hormone (TSH) $> 1.5 \times$ the upper limit of normal (ULN) at Week -5 (Visit S1). Patients stabilized on thyroid replacement therapy for at least 6 weeks prior to randomization are allowed.
8. Liver disease or dysfunction, including:
 - Positive serology for hepatitis B surface antigen (HBsAg) and/or hepatitis C antibodies (HCV-AB) at Week -5 (Visit S1); or
 - Alanine aminotransferase (ALT), aspartate aminotransferase (AST) $\geq 2 \times$ ULN, and/or total bilirubin (TB) $\geq 1.2 \times$ ULN at Week -5 (Visit S1). If TB $\geq 1.2 \times$ ULN, a reflex indirect (unconjugated) bilirubin will be obtained and if consistent with Gilbert's disease or if the patient has a history of Gilbert's Disease, the patient may be enrolled in the study.

Note: At the discretion of the investigator, a single repeat of ALT and/or AST may be completed prior to randomization. For those patients who have a repeat ALT and/or AST, the repeat value will be used to determine eligibility. Also, if test for hepatitis C antibody is positive, but reflexive test for Hepatitis C ribonucleic acid (RNA) is negative, patient can be enrolled.

9. Gastrointestinal conditions or procedures (including weight loss surgery; eg, Lap-Band[®] or gastric bypass) that may affect drug absorption
10. Hematologic or coagulation disorders or a hemoglobin (Hgb) level < 10.0 g/dL (100 g/L) at Week -5 (Visit S1)
11. Active malignancy, including those requiring surgery, chemotherapy, and/or radiation in the past 5 years. Nonmetastatic basal or squamous cell carcinoma of the skin and cervical carcinoma in situ are allowed.
12. Unexplained creatine kinase (CK) $> 3 \times$ ULN at screening up to randomization (ie, not associated with recent trauma or physically strenuous activity). Patients with an explained CK elevation must have single repeat CK $\leq 3 \times$ ULN prior to randomization.

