12.8. Safety Endpoints

The summarization of AEs will include TEAEs. TEAEs and SAEs will be summarized by SOC, severity, and relationship to study drug for each treatment group. These AE summaries will include cumulative incidence (percent of patients experiencing the AE) and patient-year adjusted incidence rates. If appropriate, absolute and relative risk differences will be calculated using both cumulative incidence and incidence rates. Deaths, withdrawal from study treatment due to AEs, and withdrawal from the study due to AEs will each be summarized by treatment group.

Clinical safety laboratories, including hematology, blood chemistry, coagulation, HbA_{1C}, glucose, and urinalysis; PE findings; vital signs; ECG readings; and weight will be summarized by the value and by change from baseline in the value (where appropriate) at each postbaseline time point.

Hepatic Safety

Liver-associated enzymes and TB will be summarized by the value and change from baseline in the value, by treatment group and visit. In addition, the number and percent of patients with abnormal values for ALT, AST, and TB will be summarized. These summaries of patients with abnormal values will be performed overall; by normal baseline; and by abnormal baseline for each of ALT, AST, and TB. Hy's law criteria ($\geq 3 \times$ ULN for either ALT or AST, with accompanying TB $> 2 \times$ ULN or patient's baseline) will also be applied to the data; any potential Hy's law cases will be listed separately. In the case of patients with Gilbert's disease, TB will be fractionated and the determination of $2 \times$ ULN based upon direct (conjugated) bilirubin. For patients with Gilbert's Disease $2 \times$ the conjugated bilirubin will be used as the criterion.

Musculoskeletal Safety

AEs of muscle-related symptoms will be summarized by treatment group. CK levels will be summarized by the value and change from baseline in the value, by treatment group and visit. In addition, the number and percent of patients with abnormal CK values will be summarized. These summaries of patients with abnormal CK will be performed overall; by normal baseline CK; and by abnormal baseline CK.

Diabetes and Hyperglycemia

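### Among patients with no history of diabetes, no stated SAP table counts new crossings of HbA1c 6.5% or fasting glucose 126 mg/dL

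*SAP*

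**What the plan says.** SAP 18.4 defines two glycemic laboratory abnormalities: "HbA1c (≥6.5%) by history of diabetes" and "Fasting Blood Glucose (≤50 mg/dL, ≥126 mg/dL) by history of diabetes". Neither refers to the baseline value. The same section also plans "Shift from baseline according to normal ranges for HbA1c and glucose by history of diabetes and visit", together with observed values and changes from baseline by visit. SAP 18.4.1 defines the categories as low, normal and high against the laboratory reference range.

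History of diabetes is a Yes/No baseline characteristic (SAP 11), and no laboratory criterion is attached to it. Protocol 7.2 excludes patients only when HbA1c at screening is 10% or more.

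Protocol 11.4 names new-onset diabetes/hyperglycemia as an adverse event of special interest. Protocol 12.8 makes adverse-event reporting the main route: "Cases of new onset of diabetes will be recorded as AEs and will be summarized using the appropriate SOC". The synopsis gives HbA1c and glucose a supporting role, "to identify potential cases of new onset of diabetes", and SAP 18.1.6 refers to the 18.4 laboratory data as a further evaluation of these events.

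**The concern.** A patient with no recorded history of diabetes and a baseline HbA1c between 6.5% and just under 10% can be randomized. If nothing changes, that patient still appears after baseline as an abnormal value in the no-history row. That row is the one that bears on new onset, and it mixes patients who crossed the limit on study with patients who entered above it.

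The plan takes account of baseline for other analytes. In the same SAP list, creatinine and one hemoglobin item are changes from baseline. Protocol 12.8 tabulates CK overall, "by normal baseline CK; and by abnormal baseline CK", and does the same for ALT, AST and total bilirubin. No such split is stated for glucose or HbA1c, although the condition they help to detect is defined by being new.

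At stake is how a reader interprets this row. Protocol 11.4 reports a Phase 2 difference in hyperglycemia (10.8% on placebo, none on 180 mg), so the comparison is of interest in either direction.

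**Working it through.** The plan states no figure for these counts, so there is none to reproduce. Its only design figure, the power for LDL-C, has no bearing here.

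**Step 1: can any planned table give new crossings?**
- *Threshold counts.* These have no baseline condition, so prevalent and new cases are mixed.
- *Shift tables.* These do condition on baseline, but at the laboratory's upper limit of normal, which the documents do not give. If that limit lies below 6.5% or 126 mg/dL, all prevalent cases fall in the baseline-high row and the normal-to-high cell is free of them. That cell then counts crossings of a lower limit, and a patient who starts high but below 6.5% and later exceeds it appears as high to high. Only if the upper limit coincided with the diabetic threshold would the shift table give the wanted count.
- *Change from baseline by visit.* This describes averages and does not count crossings.

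**Step 2: how large could the effect be?** All rates are assumptions, because the documents give neither prevalence nor incidence. In the no-history row, let p be the share already at or above the limit at baseline, equal in expectation between arms by randomization, and let i be the incidence of new crossings among the rest. Assume that patients above the limit at entry stay above it.

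- Counted proportion = p + (1 − p) × i
- Counted risk difference = (1 − p) × (difference in i)

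With i = 5% versus 3%, the true ratio is 0.05/0.03 = 1.67 and the true difference is 2.0 points.

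| p | Counted, higher arm | Counted, lower arm | Ratio | Difference (points) |
|---|---|---|---|---|
| 0% | 0.0500 | 0.0300 | 1.67 | 2.00 |
| 2% | 0.02 + 0.98 × 0.05 = 0.0690 | 0.02 + 0.98 × 0.03 = 0.0494 | 1.40 | 1.96 |
| 4% | 0.04 + 0.96 × 0.05 = 0.0880 | 0.04 + 0.96 × 0.03 = 0.0688 | 1.28 | 1.92 |
| 8% | 0.08 + 0.92 × 0.05 = 0.1260 | 0.08 + 0.92 × 0.03 = 0.1076 | 1.17 | 1.84 |

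A second set of assumed rates shows the same pattern. With 7.5% versus 5% (true ratio 1.50), the counted ratio is 1.36, 1.24 and 1.16 at p = 2%, 5% and 10%. Limiting the count to patients below the limit at baseline returns 1.50 in each case.

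**The case against.** A reader might infer from the missing baseline condition that known diabetics swamp the comparison, or that a planned test of glycemic harm is biased. The documents support neither reading.

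- *Known diabetics.* The split by history already tabulates them separately. What remains is patients with no recorded history who enter above the limit. The documents give no figure for that group, and it may be small.
- *Shift tables.* They are not useless here. They are by history and visit and condition on baseline, so they partly do what is wanted, at a different cut-off.
- *Ascertainment.* New-onset diabetes is captured mainly as an adverse event. Protocol 11.2.3 keeps conditions already present at baseline out of adverse-event reporting unless they change in severity or seriousness.
- *Testing.* SAP 18 plans no statistical comparison of safety data unless a section says otherwise, and 18.4 does not. No ratio is planned for these counts. On the difference scale the loss is only the share p.
- *Assumptions.* Prevalent patients who fall below the limit on treatment would break the stay-above assumption and could add contrast if the drug lowers glucose.
- *Unseen templates.* SAP 8 leaves table content to output templates that are not in the documents, and a baseline restriction could be stated there.

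All of this stands, and it limits the importance of the point. It does not remove the gap: the written counting rule still mixes new and prevalent cases in the no-history row, and no stated table separates them at the diabetic limits.

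**Conclusion.** The point holds for the no-history row only. As written, the SAP gives no count of new crossings of HbA1c 6.5% or fasting glucose 126 mg/dL, unless the laboratory's upper limits happen to coincide with those values. Under the assumed rates the counted ratio moves from 1.67 to between 1.40 and 1.17, while the risk difference moves only from 2.0 points to between 1.96 and 1.84. With no undiagnosed prevalent cases the two ways of counting agree.

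It would go too far to conclude that a glycemic signal would be missed. These counts are descriptive and support adverse-event ascertainment. Prevalent cases add about the same expected proportion to each arm, not the same number, because allocation is 2:1. The change is worth making because it is inexpensive and follows the baseline split that the protocol already uses for liver enzymes, bilirubin and CK.

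**What to change.** In SAP 18.4, keep the split by history of diabetes and the existing overall counts. For patients with no history of diabetes, add counts of HbA1c of 6.5% or more and of fasting glucose of 126 mg/dL or more among those with **both** baseline HbA1c below 6.5% and baseline fasting glucose below 126 mg/dL. State that denominator, and show patients already at or above either limit in a separate row. Shift tables at these two cut-offs would be an acceptable alternative.

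Both analytes are needed in the condition. Otherwise a patient who enters with an HbA1c of 6.8% and a glucose of 120 mg/dL would still count as a new glucose crossing.

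The cost is a short addition to the SAP text, one filter, one extra row and a slightly smaller denominator. HbA1c and blood chemistry are collected at Visits S1 and T1, so no new data are needed. The SAP addendum records that the planned analyses were completed and the study unblinded, so a table added now should be labelled post hoc.
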